#### 5.2.6.2.2 AE reporting to the sponsor and timelines

The investigator must report SAEs, AESIs, and non-serious AEs which are relevant for the reported SAE or AESI, on the BI SAE form via fax immediately (within 24 hours) to the sponsor's unique entry point (country specific contact details will be provided in the ISF). The same timeline applies if follow-up information becomes available. In specific occasions, the investigator could inform the sponsor upfront via telephone. This does not replace the requirement to complete and fax the BI SAE form.

With receipt of any further information to these events, a follow-up SAE form has to be provided. For follow-up information the same rules and timeline apply as for initial information. All (S)AEs, including those persisting after individual patient's end of trial must be followed up until they have resolved, have been assessed as "chronic" or "stable", or no further information can be obtained.

#### 5.2.6.2.3 Pregnancy

In rare cases, pregnancy might occur in a clinical trial. Once a patient has been enrolled in the clinical trial and has taken trial medication, the investigator must report any drug exposure during pregnancy in a trial participant immediately (within 24 hours) by means of Part A of the Pregnancy Monitoring Form to the sponsor's unique entry point. <for Japan only> Pregnancy until 6 months after the last dose of study medication should be reported as a drug exposure during pregnancy.

Similarly, potential drug exposure during pregnancy must be reported if a partner of a male trial participant becomes pregnant. This requires a written consent of the pregnant partner; in the event that consent cannot be obtained, information will be collected and reported in accordance with regulatory requirements. The ISF will contain the trial specific information and consent for the pregnant partner.

Proprietary confidential information © 2020 Boehringer Ingelheim International GmbH or one or more of its affiliated companies

The outcome of the pregnancy associated with the drug exposure during pregnancy must be followed up and reported to the sponsor's unique entry point on the Pregnancy Monitoring Form for Clinical Studies (Part B).

The ISF will contain the Pregnancy Monitoring Form for Clinical Studies (Part A and B).

As pregnancy itself is not to be reported as an AE, in the absence of an accompanying SAE and/or AESI, only the Pregnancy Monitoring Form for Clinical Studies and not the SAE form is to be completed. If there is an SAE and/or AESI associated with the pregnancy an SAE form must be completed in addition.

#### 5.2.6.2.4 Exemptions to AE reporting

##### **Collection and reporting of progressive disease**

The outcome "disease progression" is used to assess trial endpoints for the analysis of efficacy and will be recorded on the appropriate page of the eCRF.

Disease progression will not be considered as an 'always serious' AE for this study. Only if disease progression meets standard seriousness criteria (see [Section 5.2.6.1.2, Serious adverse event](#)), will it be recorded on the AE page in the eCRF as well as on the BI SAE form, and the SAE reporting process will be followed. The exemption to reporting disease progression as an AE or SAE applies when disease progression is observed on imaging in an asymptomatic patient with no clinical signs of disease progression.

However if there is evidence suggesting a causal relationship between the investigational drug and the progression of the underlying malignancy, the event must be recorded as an SAE on the AE page in the eCRF and reported as an SAE on the SAE Form.

Clinical symptoms and/or signs of disease progression will be recorded on the AE page in the eCRF. If signs and symptoms of disease progression of the patient's underlying malignancy meet standard seriousness criteria, they will additionally be reported as SAEs on the BI SAE form and SAE reporting procedures will be followed. If signs and symptoms are attributable to a diagnosis, reporting the diagnostic term is preferable (e.g. pulmonary embolism rather than dyspnoea; intestinal obstruction rather than abdominal pain).

Lab values meeting the potential severe DILI definition in [section 5.2.6.1.4](#) must always be reported as AESI, even if the most likely cause is disease progression. No exemption to AE reporting applies.

Exempted events are reviewed at appropriate intervals by the Sponsor and the SMC.

#### 5.2.6.3 Dose limiting toxicities

DLTs will be recorded throughout the trial. Any DLT must be reported to the Sponsor by the Investigator or designee within 24 hours of first knowledge using the same procedure as SAE reporting. Only DLTs occurring in the first 4 weeks (the first cycle) of treatment are considered for dose-escalation decisions made by the SMC. DLTs observed during the MTD

Proprietary confidential information © 2020 Boehringer Ingelheim International GmbH or one or more of its affiliated companies

evaluation period will be considered for MTD determination. In addition, DLT(s) observed during the ophthalmological assessment and echocardiographic assessment of Cycle 2 Day 1 will be considered for MTD determination. However, all AEs and SAEs meeting criteria of DLT observed in all treatment cycles will be considered for determining a RD.

Any of the following AEs will be classified as DLTs if assessed as possibly related to BI 3011441, i.e., unless unequivocally due to underlying malignancy or an extraneous cause and will be reviewed by the SMC.

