- s) Extended Follow-up for progressive disease visits for tumour assessment by imaging (CT scan or MRI) for patients who discontinue trial treatment without having progressive disease based on RECIST v1.1 should be performed every 8 weeks ( $\pm 4$  days) until progressive disease or another withdrawal criterion is met. At these visits, SAEs and AESIs occurring during the trial that are considered to be related to trial treatment or procedures will be followed until resolution after EOR until the individual patient's end of trial.
- t) Patients will remain hospitalised for at least three days after the first administration of BI 3011441. On day four or later, the investigator will then evaluate whether it is appropriate to discharge the patient based on the patient's condition. For this evaluation, the investigator will perform the assessment of adverse events and if necessary haematology and clinical chemistry examination.
- u) X-ray for chest region will be conducted to determine presence of interstitial lung diseases on Day 1 of Cycle 2.

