## 2. TRIAL OBJECTIVES AND ENDPOINTS

### 2.1 MAIN OBJECTIVES, PRIMARY AND SECONDARY ENDPOINTS

#### 2.1.1 Main objectives

The primary objective of this trial is to confirm the safety and tolerability of previously identified MTD, BI 3011441 8mg (in Caucasian FIH study) as a single agent when administered orally to adult Japanese patients with NRAS/KRAS mutation positive advanced or metastatic refractory solid tumours.

The MTD will be determined based on the frequency of patients experiencing DLTs during the MTD evaluation period. The MTD evaluation period is defined as first treatment cycle (28 days). At the end of the dose escalation, the BLRM will be rerun using all DLTs. This result as well as all available data will be used to define the recommended dose (RD).

The secondary objectives is to evaluate the safety and tolerability, and characterise PK of BI 3011441 as monotherapy in Japanese patients with NRAS/KRAS mutation positive advanced solid tumours

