#### 2.1.2 Primary endpoint(s)

- MTD defined as the highest dose with less than 25% risk of the true DLT rate being equal or above 33% during the MTD evaluation period. For the definition of DLTs, refer to [Section 5.2.6.3](#)
- Number of patients with DLTs in the MTD evaluation period.

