  - After holding the trial drug and obtaining a follow-up echocardiography within 4 weeks, LVEF has returned within the normal institutional range or to within 5 percentage points of the screening value, but on re-challenge there is second decline of an absolute decrease in LVEF of 10 percentage points or greater from screening value, whether above or below institutional LLN.
- Symptomatic heart failure
- Any retinopathy  $\geq$  Grade 2
- Retinal vein occlusion of any grade.
- Interstitial lung disease/pneumonitis of any grade
- Hepatic injuries assessed as related to trial drug and which meet the AESI criteria for hepatic injury in [Section 5.2.6.1.4](#)
- Treatment pause of BI 3011441 for  $\geq$ 14 days, or dose reduction in Cycle 1 due to treatment-related AEs
- Any treatment-related  $\geq$  Grade 2 toxicity that persists and results in a more than 2 weeks delay of administration of BI 3011441 on Cycle 2 Day 1
- Any treatment-related AE that would require permanent discontinuation of BI 3011441.

Any other toxicity considered significant enough to be qualified as DLT in the opinion of the Investigators, and confirmed by the SMC, will be reported as a DLT.

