6. GENERAL ANALYSIS DEFINITIONS

6.1 TREATMENT

The trial is an open-label phase I trial with dose escalation, confirmation and expansion of BI 3011441 as monotherapy. For basic study information such as treatments to be administered, assignment of treatment groups, and selection of doses, see CTP Section 4.

For safety analyses, AEs will be classified to one of the following time periods: “Screening”, “On-treatment” or “Follow-up.” This will be applied for all adverse events. Detailed rule for assigning AEs to these time periods are listed below.

- If the date of informed consent \leq AE onset date $<$ date/time of first administration of trial treatment, then the AE is assigned to “Screening”;
- If date of first administration of trial treatment \leq AE onset date \leq date of last administration of trial treatment + 30 days of Residual Effect Period (REP), then the AE is assigned to “On-treatment”;
- If AE onset date $>$ date of last administration of trial treatment + 30 days, then the AE is assigned to “Follow-up”

Table 6.1: 1 Definition of analysis treatment periods for safety analysis

Analysing Treatment Period	Start Date	Stop Date
Screening	Date of informed consent	Date/Time of the first administration of trial treatment
On-treatment	Date of the first administration of trial treatment	Date of the last administration of trial treatment + 30 days of REP
Follow-up	Date of the last administration of trial treatment + 31 days	Date of the last visit
MTD evaluation period*	Date of the first administration of trial treatment	Date of the first administration of trial treatment + 28 days (i.e., treatment cycle)

*The MTD evaluation period is only applied to the patients in the dose escalation part of the trial.

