6.7 BASELINE, TIME WINDOWS AND CALCULATED VISITS

Unless otherwise specified baseline is defined as the time point closest to but prior to the first administration of any study medication. If no time is specified and the date is the same as the first administration date, then it will still be considered baseline if not specified otherwise. If there is no measurement earlier than the first administration of study medication, then no baseline will be derived.

For laboratory parameters for which not only the examination date but also the sampling time was recorded, examination time should be taken into consideration when defining baseline. That is a laboratory measurement on the same date as the first administration of study treatment is considered as baseline if and only if the examination time of this laboratory measurement is before the first administration of study treatment. If any of these times is missing and the date of laboratory assessment is the same as the date of first administration of study medication, then the laboratory assessment will be considered as according to protocol, i.e., as prior to first study medication.

Study days and visits will be labelled according to the flow charts in the CTP. Study day will be calculated relative to the date of the first administration of study drug. The day prior to first

administration of study drug will be 'Day -1' and the day of first administration of study drug will be 'Day 1'; therefore 'Day 0' will not exist.

Imaging time windows:

Time windows and visits will be calculated to determine the planned day of tumour measurement and response status, based on the protocol-specified tumour imaging schedule.

For the presentation of tumour response data which will follow a calculated visit approach based on the protocol specified tumour imaging schedule: Imaging will be performed at screening and every 8 weeks after the first administration of study treatment (i.e. Week 8, 16, 24 etc.). Image data will be slotted to Week 8, 16, 24 etc. based on their relative study day (from start of treatment) and using a ± 4 week window (e.g., images taken in the first 6 weeks from start of treatment will be assigned to Week 8). If two or more images for a patient are assigned to one interval then the last assessment will be used to ensure PD is not missed.

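### ILD first found on the Cycle 2 Day 1 chest X-ray can miss the MTD and the primary DLT count, because the sentence carrying that visit's findings in names only the eye and echo assessments

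*Protocol*

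**What the plan says.** **DLT definition.** The non-haematologic list in protocol Section 5.2.6.3 includes "Interstitial lung disease/pneumonitis of any grade", so a symptom-free Grade 1 case qualifies if possibly related to the drug.

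**The test.** Flow chart footnote u: "X-ray for chest region will be conducted to determine presence of interstitial lung diseases on Day 1 of Cycle 2". The flow chart gives that visit a window of ±2 days.

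**The period.** Protocol Section 2.1.1: "The MTD evaluation period is defined as first treatment cycle (28 days". The second primary endpoint in Section 2.1.2 is "Number of patients with DLTs in the MTD evaluation period", and Section 7.3.2 fits the main MTD model to DLT data from the same period.

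**Two counting sentences in Section 5.2.6.3.** For escalation: "Only DLTs occurring in the first 4 weeks (the first cycle) of treatment are considered for dose-escalation decisions made by the SMC". For the MTD, the first-cycle DLTs are supplemented by this: "DLT(s) observed during the ophthalmological assessment and echocardiographic assessment of Cycle 2 Day 1 will be considered for MTD determination".

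**The SAP.** Table 6.1:1 gives the stop date of the MTD evaluation period as "Date of the first administration of trial treatment + 28 days (i.e., treatment cycle". Section 6.7 numbers the first dosing day as Day 1, with no Day 0. The SAP sections on the MTD (5.1, 6.1, 6.3, 7.4.1 and 7.8.1.1) do not restate the carry-in sentence.

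**The concern.** Three safety checks that can reveal a DLT fall at the same visit: eye, echo and chest X-ray. Two are carried into the MTD determination by name and the third is not. A patient who completes Cycle 1 is evaluable for the MTD. If ILD is then first seen on the X-ray, read literally, that patient enters the BLRM as a non-DLT. The error can only be an undercount.

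The X-ray has at least as good a claim to be carried in as the echo. LVEF is also measured on Day 15 of Cycle 1, whereas no chest X-ray is scheduled in Cycle 1. As the text stands, the day within the visit window can decide whether the same radiological finding counts towards the primary endpoint. The two documents also disagree about the nominal day.

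**Working it through.** **Step 1: calendar.** The cycle is 28 days and the first dose is Day 1, so Cycle 2 Day 1 is nominally Day 28 + 1 = 29. With ±2 days the window is Day 27 to 31. The protocol period is Days 1 to 28. The SAP stop date is first dose + 28 days = Day 1 + 28 = Day 29.

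| X-ray done on | Protocol period | SAP period |
|---|---|---|
| Day 27 or 28 | inside | inside |
| Day 29 (nominal) | outside | inside |
| Day 30 or 31 | outside | outside |
| Later, if Cycle 2 is delayed | outside | outside |

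Where a cell says outside, only a carry-in sentence could bring the finding into the MTD data, and the existing one does not name the X-ray.

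**Step 2: reproduce the plan's model.** Inputs are from protocol Section 7.1 and Table 7.1:2:
- logit(π_d) = log α + β log(d/8).
- The prior on (log α, log β) is a three-part normal mixture. Weights are 0.8, 0.1 and 0.1; means (−0.94, 0.61), (0.85, 0.79) and (−2.20, 0.80); SDs (0.91, 0.91), (2, 1) and (2, 1); correlations −0.08, 0 and 0.
- The posterior is proportional to the prior times the product over doses of π_d^x (1 − π_d)^(n − x).
- The EWOC criterion requires P(π_d ≥ 0.33) < 0.25.

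Grid integration gives prior overdose probabilities at 4, 6, 7 and 8 mg of 0.129, 0.232, 0.310 and 0.422. Table 7.1:3 states 0.128, 0.233, 0.310 and 0.422, so the model is reproduced.

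**Step 3: effect of one omitted event on the MTD.** With 0/3 at 4 mg and 0/3 at 6 mg:

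| Data at 8 mg | P(overdose) at 8 mg, Table 10.2:1 | Recomputed | Table recommendation |
|---|---|---|---|
| 1/6 (scenario 20) | 0.106 | 0.103 | 8 mg |
| 2/6 (scenario 21) | 0.274 | 0.268 | 7 mg |

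This is an MTD decision. In scenario 20, 3 + 3 + 6 = 12 patients have been treated, 6 of them at 8 mg, which meets the second MTD criterion of Section 7.1. Appendix 10.2 says that 8 mg could be declared the MTD there. With the extra event, 8 mg fails the 0.25 limit.

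A second pair, at 6 mg after 0/3 at 4 mg, behaves the same way. Going from 2/6 to 3/6 moves the overdose probability at 6 mg from 0.178 to 0.397 (scenarios 9 and 10; recomputed 0.185 and 0.407), and the recommendation goes from 6 mg to 4 mg.

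**Step 4: how typical is this?** Table 10.2:1 contains 14 steps that add one DLT at 8 mg with all else fixed: 16→17, 17→18, 19→20, 20→21, 21→22, 32→33, 34→35, 35→36, 37→38, 39→40, 40→41, 42→43, 44→45 and 45→46. The recommended dose changes in two of them (17→18 and 20→21). One event can change the MTD; it usually would not at 8 mg.

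**The case against.** Several points on the other side stand and limit the claim.

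- **The SAP period reaches Day 29.** A reader might infer that ILD found on this X-ray is always excluded from the primary endpoint. The documents do not support that. Days 27 and 28 are inside both periods, and Day 29 is inside the SAP's.
- **The X-ray is not the only early check.** Oxygen saturation is listed among the vital signs (Section 5.2.2), which are taken at every Cycle 1 visit, but it is measured only if needed. The flow chart also marks a tumour assessment at Cycle 2, which would include chest CT, although Section 5.1 puts the first one at week 8. The X-ray is the only ILD-specific imaging. A CT at that visit would be missed by the carry-in sentence too.
- **The event is not lost.** It is reported within 24 hours, counts for the RD and the on-treatment DLT endpoint, enters the end-of-escalation BLRM rerun (Section 2.1.1), and can be discussed by the SMC with other data from beyond the period (Section 4.1.2). These routes serve the RD and safety review. The primary endpoints remain the MTD and the DLT count in the MTD evaluation period.
- **Oversight is not proven.** Amendment 1 added the X-ray and also updated the DLT condition for MTD evaluation to avoid underestimating DLTs. A reader might infer that this purpose belongs to the eye and echo sentence and that the X-ray was forgotten. The log does not identify that sentence, so omission by choice cannot be ruled out.
- **Scenarios 6 and 7 are not evidence for this point.** They differ by one DLT at 6 mg and lead to different next doses. They are escalation decisions, governed by the separate first-4-weeks sentence, and adding the X-ray to the MTD sentence would not alter them.
- **ILD is described as rare** in Table 1.4.2:1, and the documents give no frequency for a case first seen at this visit.

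**Conclusion.** The gap is real but conditional. ILD first found on the scheduled X-ray can be left out of the MTD and the primary DLT count: on Days 29 to 31 under the protocol, on Days 30 to 31 under the SAP, and at a delayed visit under either. On the nominal day itself the documents conflict. The direction is always an undercount. One event can be enough to move 8 mg across the EWOC limit (0.106 to 0.274 against 0.25), although in most of the tabulated 8 mg steps one event does not change the recommendation.

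This rests on three assumptions: the ILD is judged possibly related, its onset is dated to the X-ray, and the counting sentences are applied as written. An onset dated back into Cycle 1 would count, but no rule found in either document provides for such dating. How often the situation would arise cannot be estimated from the documents. The amendment is worth making because a stated counting rule for a primary endpoint is incomplete and the correction is small.

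**What to change.** Reconcile flow chart footnote u, protocol Sections 2.1.1 and 5.2.6.3, and SAP Table 6.1:1, so that one counting rule covers all scheduled Cycle 2 Day 1 safety assessments:

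1. In Section 5.2.6.3, add the chest X-ray (ILD) to the eye and echo assessments whose Cycle 2 Day 1 findings enter the MTD determination.
2. In the SAP, use the same list and the same period end as the protocol when defining the DLTs that enter the MTD set data, the BLRM and the primary DLT count.
3. State whether that list also applies to the sentence restricting dose-escalation decisions to the first 4 weeks. If it does not, say so explicitly.

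The cost is a few words in each document. The X-ray is already scheduled, so no procedure is added. The downside is a possible extra DLT in the model, and hence a more cautious recommendation in some data sets.

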#### Haematologic

- CTCAE Grade 4 neutropenia ( $<500/\text{mm}^3$ ) lasting  $>7$  days without documented infection.
- CTCAE Grade  $\geq 3$  neutropenia ( $<1000/\text{mm}^3$ ) with documented infection.
- CTCAE Grade  $\geq 3$  febrile neutropenia, where Grade 3 febrile neutropenia is defined as ANC  $<1000/\text{mm}^3$  and a single temperature of  $>38.3^\circ\text{C}$  ( $101^\circ\text{F}$ ) or a sustained temperature of  $\geq 38^\circ\text{C}$  ( $100^\circ\text{F}$ ) for more than one hour; Grade 4 neutropenia is defined as life-threatening consequences or urgent intervention indicated; and Grade 5 neutropenia is defined as a fatal neutropenia
- CTCAE Grade 3 thrombocytopenia ( $\geq 25,000/\text{mm}^3$  and  $<50,000/\text{mm}^3$ ) associated with bleeding
- CTCAE Grade 4 ( $<25,000/\text{mm}^3$ ) thrombocytopenia
- Thrombocytopenia or anaemia requiring transfusion per local or international guidelines.

#### Non-haematologic

- Grade  $\geq 3$  non-haematologic (not laboratory) toxicities despite the use of adequate medical interventions and/or prophylaxis as dictated by local institutional clinical practices, the clinical trial protocol, and/or the judgment of the Investigator. The following exceptions apply:
  - In a patient with pre-existing fatigue at baseline, Grade 3 fatigue will only be considered as a DLT if it lasts for more than 7 days despite adequate medical interventions and baseline fatigue was no more than Grade 1.
  - Grade 3 nausea or Grade 3 vomiting will be defined as a DLT when it persists at Grade 3 longer than 48 hours despite adequate medical intervention
  - Grade  $\geq 3$  diarrhea will be defined as a DLT only when hospitalisation is required, and the event persists at Grade  $\geq 3$  for more than 48 hours despite adequate medical intervention.
  - Hypertension will be defined as a DLT only when a patient was enrolled with controlled hypertension as per the exclusion criteria, and systolic blood pressure has increased  $\geq 160$  mm Hg or diastolic blood pressure increased  $\geq 100$  mm Hg, which cannot be controlled by hypertensive medication and which requires a dose reduction / discontinuation of study drug.
- Any Grade 3 or Grade 4 non-haematologic laboratory value if:
  - Medical intervention is required to treat the patient, except Grade 3 electrolyte abnormality that lasts  $<72$  hours, is not clinically complicated and resolves spontaneously or responds to conventional medical intervention, or
  - The abnormality leads to hospitalisation, or
  - The abnormality persists for  $>1$  week, and considered significant enough to be qualified as DLT in the opinion of the Investigator, and confirmed by the SMC.

Proprietary confidential information © 2020 Boehringer Ingelheim International GmbH or one or more of its affiliated companies

- An absolute decrease in LVEF of 10 percentage points or greater from screening value to a value that is below institutional LLN value, OR an absolute decrease in LVEF of 15 percentage points or greater whether below or above institutional LLN, even if the patient is asymptomatic, will be defined as a DLT if:
  - After holding the trial drug and obtaining a follow-up echocardiography within 4 weeks, LVEF has not returned within the normal institutional range or to within 5 percentage points of the screening value; OR
  - After holding the trial drug and obtaining a follow-up echocardiography within 4 weeks, LVEF has returned within the normal institutional range or to within 5 percentage points of the screening value, but on re-challenge there is second decline of an absolute decrease in LVEF of 10 percentage points or greater from screening value, whether above or below institutional LLN.
- Symptomatic heart failure
- Any retinopathy  $\geq$  Grade 2
- Retinal vein occlusion of any grade.
- Interstitial lung disease/pneumonitis of any grade
- Hepatic injuries assessed as related to trial drug and which meet the AESI criteria for hepatic injury in [Section 5.2.6.1.4](#)
- Treatment pause of BI 3011441 for  $\geq$ 14 days, or dose reduction in Cycle 1 due to treatment-related AEs
- Any treatment-related  $\geq$  Grade 2 toxicity that persists and results in a more than 2 weeks delay of administration of BI 3011441 on Cycle 2 Day 1
- Any treatment-related AE that would require permanent discontinuation of BI 3011441.

Any other toxicity considered significant enough to be qualified as DLT in the opinion of the Investigators, and confirmed by the SMC, will be reported as a DLT.

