Drug-induced liver injury (DILI)	Rare but potentially severe event with all drugs in development.	As DILI is an adverse events of special interest (AESI), there will be timely detection, evaluation, and follow-up of pre-specified liver laboratory parameters to ensure patients' safety.
Interstitial Lung Disease	Rare but potentially severe event observed with [REDACTED] [REDACTED].	Patients with pre-existing interstitial lung disease are excluded.
Hypertension	Observed with [REDACTED] [REDACTED].	Patients with uncontrolled hypertension are excluded. Vital signs will be monitored at each trial visit.
Rhabdomyolysis	Observed with [REDACTED] [REDACTED].	Patients with CPK $\geq$ 2.5 x ULN are excluded. CPK level will be monitored.
Photosensitivity	Observed with [REDACTED] [REDACTED].	Patients will be instructed to avoid direct sun light.
Trial procedures		
[REDACTED]	[REDACTED]	[REDACTED]

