as: Blood pressure measured in a rested and relaxed condition, where systolic BP  $\geq 140$  mmHg, or diastolic BP  $\geq 90$  mmHg, with or without medication.

9. Left ventricular ejection fraction (LVEF)  $< 50\%$ .
10. Baseline QT interval corrected for heart rate using Fridericia's formula (QTcF)  $> 470$  msec or congenital long QT syndrome
11. Previous or concomitant malignancies at other sites, except effectively treated
  - Non-melanoma skin cancers
  - Carcinoma *in situ* of the cervix
  - Ductal carcinoma *in situ*
  - Other malignancy that has been in remission for more than 3 years and is considered to be cured.
12. Leptomeningeal carcinomatosis.
13. Presence or history of uncontrolled or symptomatic brain metastases, unless considered stable by the investigator and local therapy was completed. Use of corticosteroids is allowed if the dose was stable for at least 4 weeks. Inclusion of patients with newly identified brain metastasis/es at screening will be allowed if patients are asymptomatic.
  - Patients who have resected brain metastases, or have received radiation therapy that finished at least 4 weeks (whole brain radiation) or 2 weeks (stereotactic body radiotherapy) prior to treatment of the trial are considered eligible if they meet all of the following criteria:
    - a) Residual neurological symptoms CTCAE grade  $\leq 2$
    - b) Are taking stable doses of dexamethasone, if applicable
    - c) Follow-up magnetic resonance imaging (MRI) shows no new lesions
14. Known pre-existing interstitial lung disease
15. Known active hepatitis B infection (defined as presence of Hep B sAg and/or Hep B DNA), active hepatitis C infection (defined as presence of Hep C RNA)
16. Active infectious disease which puts the patient at increased risk in the opinion of the investigator
17. Any history or presence of uncontrolled gastrointestinal disorders that could affect the intake and/or absorption of the study drug (e.g. nausea, uncontrolled vomiting, Crohn's disease, ulcerative colitis, chronic diarrhoea, malabsorption) in the opinion of the investigator.
18. Patients not expected to comply with the protocol requirements or not expected to complete the trial as scheduled (e.g. chronic alcohol or drug abuse or any other condition that, in the investigator's opinion, makes the patient an unreliable trial participant).

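### The hypertension DLT clause turns on baseline hypertension status, uses an undefined entry category and is not ranked against the general DLT items, so some events count in one group of patients and not in the other

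*Protocol*

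**What the plan says.** The non-haematologic DLT list in Protocol section 5.2.6.3 opens with a general rule for Grade 3 or higher toxicities. It then says "The following exceptions apply". Hypertension is one of these exceptions: "Hypertension will be defined as a DLT only when a patient was enrolled with controlled hypertension as per the exclusion criteria". The clause goes on to require a blood pressure of at least 160 mmHg systolic or 100 mmHg diastolic, "which cannot be controlled by hypertensive medication and which requires a dose reduction / discontinuation of study drug".

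The criterion it points to, in section 3.3.3, defines uncontrolled hypertension only: "systolic BP $\geq 140$ mmHg, or diastolic BP $\geq 90$ mmHg, with or without medication". Controlled hypertension is not defined there.

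Further down the same list stand separate items that do not mention hypertension:
- a treatment pause of 14 days or more, or a "dose reduction in Cycle 1 due to treatment-related AEs";
- a toxicity of Grade 2 or higher that delays Cycle 2 Day 1 by more than two weeks;
- "Any treatment-related AE that would require permanent discontinuation of BI 3011441";
- a closing provision beginning "Any other toxicity considered significant enough to be qualified as DLT in the opinion of the Investigators", which needs SMC confirmation.

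Hypertension is a listed risk in Table 1.4.2:1, where the mitigation reads "Patients with uncontrolled hypertension are excluded. Vital signs will be monitored at each trial visit".

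**The concern.** Enrolled patients fall into two groups: those with treated hypertension below the exclusion limits, and those without hypertension. Read literally, the clause names only the first. Because it is an exception, it takes the second group out of the general Grade 3 rule and puts nothing in its place. No reason is given.

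The neighbouring fatigue exception works the other way. It raises the bar for patients who already have the condition and leaves everyone else under the general rule. That contrast suggests a drafting slip.

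DLTs in the MTD evaluation period are a primary endpoint and the only toxicity input to the BLRM that guides escalation. DLTs in all cycles are a secondary endpoint (Protocol 2.1.3; SAP 5.2.2 and 7.5.2) and bear on the recommended dose (Protocol 2.1.1 and 5.2.6.3). With cohorts of three, the count should not depend on which patients happen to have background hypertension.

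**Working it through.** **Step 1. Which events are counted differently?** Take drug-related hypertension that meets the blood-pressure and medication conditions and needs a dose reduction or discontinuation. Assume the general items apply alongside the hypertension clause.

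| Course of the event | Controlled hypertension at entry | No hypertension at entry |
|---|---|---|
| Dose reduced within Cycle 1 | DLT | DLT, reduction item |
| Paused 14 days or more, starting in Cycle 1 | DLT | DLT, pause item |
| Drug permanently stopped, any cycle | DLT | DLT, discontinuation item |
| (a) Onset late in Cycle 1, held under 14 days, reduced dose started in Cycle 2 | DLT | No automatic item |
| (b) Onset in Cycle 2 or later, held under 14 days, dose reduced | DLT | No automatic item |

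Example of (a): onset on Day 22, held for about seven days, resumed one level lower in Cycle 2. The reduction is not in Cycle 1, the pause is under 14 days, Cycle 2 is not delayed by more than two weeks, and the drug is not stopped. The hypertension clause asks only that the event require a reduction and sets no time limit, so the same course counts in a patient with controlled hypertension. The Grade 3 row of Table 4.1.4.2:1 (interrupt, then reduce) makes this sequence possible.

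Rows (a) and (b) arise only above 4 mg. At 4 mg no reduction is allowed and the drug is stopped (section 4.1.4.2), so the discontinuation item applies.

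An event that needs neither reduction nor discontinuation fails the hypertension clause in both groups, so that gap is not differential.

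**Step 2. What does one DLT do to the model?** Inputs are from Protocol section 7.1: logit(p_d) = log α + β·log(d/8), with a bivariate normal mixture prior on (log α, log β):
- weight 0.8, mean (−0.94, 0.61), SD (0.91, 0.91), correlation −0.08;
- weight 0.1, mean (0.85, 0.79), SD (2, 1), correlation 0;
- weight 0.1, mean (−2.20, 0.80), SD (2, 1), correlation 0.

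The posterior is proportional to the prior × ∏ p_d^k (1 − p_d)^(n−k), integrated on a 1401 × 1001 grid. P(OD) is the posterior probability that p_d ≥ 0.33, and the limit is 0.25.

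Reproducing the plan first: prior P(OD) at 4, 6, 7 and 8 mg is 0.129, 0.232, 0.310 and 0.418, against 0.128, 0.233, 0.310 and 0.422 in Table 7.1:3. Over 17 scenarios of Table 10.2:1, current-dose P(OD) differs from the table by at most 0.012.

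| Data (DLTs/patients) | Scenario | Computed P(OD) | Stated P(OD) | Recommendation |
|---|---|---|---|---|
| 4 mg 0/3, 6 mg 1/3 | 7 | 6 mg 0.148; 7 mg 0.276; 8 mg 0.426 | 6 mg 0.153 | stay at 6 mg |
| 4 mg 0/3, 6 mg 0/3 | 6 | 6 mg 0.027; 7 mg 0.074; 8 mg 0.194 | 6 mg 0.027; 8 mg 0.185 | 8 mg |
| 4 mg 0/3, 6 mg 0/3, 8 mg 2/6 | 21 | 8 mg 0.262 | 8 mg 0.274 | 7 mg |
| 4 mg 0/3, 6 mg 0/3, 8 mg 1/6 | 20 | 8 mg 0.100 | 8 mg 0.106 | 8 mg |

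If one true DLT at 6 mg went uncounted, scenario 7 would be read as scenario 6. The model would recommend 8 mg, where P(OD) on the true data is 0.426. At 8 mg, losing one of two DLTs in six patients moves P(OD) from 0.262 to 0.100, across the limit.

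**Step 3. How likely is a lost event?** The documents do not say. Let r be an assumed per-patient probability of an event that goes uncounted. The chance of at least one in six patients is 1 − (1 − r)^6, which is 11.4%, 26.5% and 46.9% for r = 2%, 5% and 10%. These are illustrations of scale only.

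**The case against.** A reader might infer from the word only that severe drug-related hypertension in a previously normotensive patient is never a DLT, and that the primary endpoint is therefore biased downwards. The documents do not support that. Section 5.2.6.3 classifies an event as a DLT if it meets any listed item, and the hypertension clause is an exception under one of them. Nothing says that it overrides the others. The clause itself requires a dose reduction or discontinuation, and in Cycle 1 either of these triggers a general item whatever the baseline status. This part of the objection stands and removes most of the apparent loss in the primary endpoint.

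The reference to the exclusion criteria could also mean not uncontrolled at entry, which would cover everyone enrolled. That may be the intent, but the words name patients with controlled hypertension, and section 3.3.3 does not define that group.

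Escalation is not automatic either. The SMC sees all Grade 2 or higher toxicity in the cohort (section 4.1.2) and weighs other information with the model (section 3.1). This is a real safeguard for dose decisions, but it does not alter the DLT count entered in the BLRM or reported as an endpoint.

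The closing provision could catch rows (a) and (b). It is discretionary, needs SMC confirmation, and is worded for other toxicities, so it is unclear whether it reaches one that the list has already restricted.

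**Conclusion.** The point holds in a limited form. The clause uses an undefined entry category and conflicts with the general items unless their order is stated.

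- **General items apply in full:** the differential loss is confined to rows (a) and (b). Row (a) touches the MTD count narrowly. Row (b) affects the all-cycle DLT endpoint and the recommended dose.
- **The word only overrides them:** the loss extends to all related hypertension in patients without hypertension at entry, and a single lost event can change the recommended dose as in step 2.

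The documents do not establish that any event would be lost. The model figures are conditional on one being lost, and the event rates are assumed. The share of patients without hypertension is not given. The finding is an inconsistency worth correcting, not a demonstrated bias in the primary endpoint.

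**What to change.** Reconcile the hypertension clause in section 5.2.6.3 with the general DLT items and with section 3.3.3, so that classification does not depend on baseline hypertension status. Two ways are to remove the enrolment-status condition, or to replace it with wording that covers every enrolled patient. State which item prevails when an exception and a general item both apply.

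While doing so, reconcile the section 4.1.4.2 text, which allows resumption at the same dose or one level lower after a pause of up to two weeks, with the Grade 3 row of Table 4.1.4.2:1, which calls for a reduction. That choice decides whether an event meets the clause. The blood-pressure thresholds and management conditions are for the sponsor to settle.

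The cost is a short protocol amendment. Vital signs are already scheduled at every Cycle 1 visit, so no data collection is added. The downside is that slightly more events may count as DLTs.
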